Upon arrival to the clinic on the day of the study visit, prior to the application of the reference and test devices, skin inspection of the application site will be conducted. The CPM Device will then be applied to the participant's chest as described in the IFU materials supplied with the device (the study team will also have received training on the proper placement of the device prior to the initiation of the study). This device will be worn for the entirety of the clinic visit (without removal and replacement). The reference device will also be used for each measurement taken during the visit, concurrently. On the CRF, the time that the CPM Device is placed on the chest will be denoted.

A Baseline measurement will then be initiated using the CPM Mobile Application in order to assign a system-generated patient ID to the participant as well as to establish the tilt angle for the following measurements. The first half of the measurement should be in the Fowler, sitting-upright position, and the second position should be in a Supine, lying-flat position. The reference device will also be used during this time to establish a respiration baseline.

The exercises below will then be followed, with the time of the start of each exercise recorded in the CRF. Four different versions of the exercises (Procedures A-D) will be available that differ only in the sequence of the measurements. The study staff will randomly select a procedure version, using the EDC. Only one procedure version per subject is used. The selected version for each subject will be recorded.

Each exercise will last approximately 4 minutes, or the time that it takes to complete one full measurement with the CPM device in measurement mode (initiated by the CPM mobile app). Within each measurement, participants will move through two positions, both upright and supine. Reference respiration data will be taken concurrently with the CPM device measurement. For each measurement, it is ensured that the reference device recordings are stabilized before initiating the CPM measurement sequence.

For items 1-17, capnography waveform and breath-by-breath reference tidal volume from a metabolic cart will be simultaneously recorded for comparison. For item 18, a diagnostic ECG and clinical grade temperature sensor data will be collected simultaneously.

<Procedure A>

Item	Respiration Rate	Tidal Volume	Mode	Duration
1	Natural (baseline)	Natural (baseline)	Doctor Setup, App	4 min

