2	15 BPM	Natural	Doctor Setup, App	4 min
3	30 BPM	Natural	Doctor Setup, App	4 min
4	40 BPM	Natural	Doctor Setup, App	4 min
5	6 BPM	Natural	Doctor Setup, App	4 min
6	25 BPM	Natural	Doctor Setup, App	4 min
7	10 BPM	Natural	Doctor Setup, App	4 min
8	35 BPM	Natural	Doctor Setup, App	4 min
9	20 BPM	Natural	Doctor Setup, App	4 min
Replace Adhesives				3 min

10	Natural	Natural (~500mL, peak-to-peak)	Doctor Setup, App	4 min
11	Natural	Shallow breaths (~ 250mL)	Doctor Setup, App	4 min
12	Natural	Deep breaths (~ 750 mL)	Doctor Setup, App	4 min
13	Natural	Extremely deep “yoga” breaths (~ 1000 mL)	Doctor Setup, App	4 min
14	15 BPM	Natural	Doctor Setup, App	4 min
15	10 BPM	Natural	Doctor Setup, App	4 min
16	30 BPM	Natural	Doctor Setup, App	4 min
17	25 BPM	Natural	Doctor Setup, App	4 min
18	Natural	Natural, ECG and skin temperatures are measured. (Simultaneous Recording with reference devices)	Doctor Setup, App	4 min

<Procedure B>

Item	Respiration Rate	Tidal Volume	Mode	Duration
1	Natural (baseline)	Natural (baseline)	Doctor Setup, App	4 min
2	30 BPM	Natural	Doctor Setup, App	4 min
3	40 BPM	Natural	Doctor Setup, App	4 min
4	6 BPM	Natural	Doctor Setup, App	4 min
5	15 BPM	Natural	Doctor Setup, App	4 min
6	10 BPM	Natural	Doctor Setup, App	4 min
7	35 BPM	Natural	Doctor Setup, App	4 min
8	20 BPM	Natural	Doctor Setup, App	4 min
9	25 BPM	Natural	Doctor Setup, App	4 min
Replace Adhesives				3 min
10	Natural	Shallow breaths (~ 250mL)	Doctor Setup, App	4 min
11	Natural	Deep breaths (~ 750 mL)	Doctor Setup, App	4 min
12	Natural	Extremely deep “yoga” breaths (~ 1000 mL)	Doctor Setup, App	4 min
13	Natural	Natural (~500mL, peak-to-peak)	Doctor Setup, App	4 min
14	10 BPM	Natural	Doctor Setup, App	4 min
15	30 BPM	Natural	Doctor Setup, App	4 min
16	25 BPM	Natural	Doctor Setup, App	4 min
17	15 BPM	Natural	Doctor Setup, App	4 min
18	Natural	Natural, ECG and skin temperatures are measured. (Simultaneous Recording with reference devices)	Doctor Setup, App	4 min

<Procedure C>

Item	Respiration Rate	Tidal Volume	Mode	Duration
1	Natural (baseline)	Natural (baseline)	Doctor Setup, App	4 min
2	40 BPM	Natural	Doctor Setup, App	4 min
3	6 BPM	Natural	Doctor Setup, App	4 min

4	15 BPM	Natural	Doctor Setup, App	4 min
5	30 BPM	Natural	Doctor Setup, App	4 min
6	35 BPM	Natural	Doctor Setup, App	4 min
7	20 BPM	Natural	Doctor Setup, App	4 min
8	15 BPM	Natural	Doctor Setup, App	4 min
9	10 BPM	Natural	Doctor Setup, App	4 min
Replace Adhesives				3 min

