10	Natural	Deep breaths (~ 750 mL)	Doctor Setup, App	4 min
11	Natural	Extremely deep "yoga" breaths (~ 1000 mL)	Doctor Setup, App	4 min
12	Natural	Natural (~500mL, peak-to-peak)	Doctor Setup, App	4 min
13	Natural	Shallow breaths (~ 250mL)	Doctor Setup, App	4 min
14	30 BPM	Natural	Doctor Setup, App	4 min
15	25 BPM	Natural	Doctor Setup, App	4 min
16	15 BPM	Natural	Doctor Setup, App	4 min
17	10 BPM	Natural	Doctor Setup, App	4 min
18	Natural	Natural, ECG and skin temperatures are measured. (Simultaneous Recording with reference devices)	Doctor Setup, App	4 min

<Procedure D>

Item	Respiration Rate	Tidal Volume	Mode	Duration
1	Natural (baseline)	Natural (baseline)	Doctor Setup, App	4 min
2	6 BPM	Natural	Doctor Setup, App	4 min
3	15 BPM	Natural	Doctor Setup, App	4 min
4	30 BPM	Natural	Doctor Setup, App	4 min
5	40 BPM	Natural	Doctor Setup, App	4 min
6	20 BPM	Natural	Doctor Setup, App	4 min
7	25 BPM	Natural	Doctor Setup, App	4 min
8	10 BPM	Natural	Doctor Setup, App	4 min
9	35 BPM	Natural	Doctor Setup, App	4 min
Replace Adhesives				3 min
10	Natural	Extremely deep "yoga" breaths (~ 1000 mL)	Doctor Setup, App	4 min
11	Natural	Natural (~500mL, peak-to-peak)	Doctor Setup, App	4 min
12	Natural	Shallow breaths (~ 250mL)	Doctor Setup, App	4 min
13	Natural	Deep breaths (~ 750 mL)	Doctor Setup, App	4 min
14	25 BPM	Natural	Doctor Setup, App	4 min
15	15 BPM	Natural	Doctor Setup, App	4 min
16	10 BPM	Natural	Doctor Setup, App	4 min
17	30 BPM	Natural	Doctor Setup, App	4 min

18	Natural	Natural, ECG and skin temperatures are measured. (Simultaneous Recording with reference devices)	Doctor Setup, App	4 min
----	---------	--	-------------------	-------

To ensure synchronization between reference device's time and CPM system's time, timestamps from each device will be recorded at the beginning of each CPM reading. Additionally, a pre-determined maneuver can be performed on or before item #1, and on or after item #18 during upright position, and corresponding clock time in the reference devices will also be logged.

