A single metered breathing app or metronome will be used to pace respiration rates throughout the study. The same breathing pacing method will be used across all patients. It is assumed that actual respiration rates will differ slightly from those described in the protocol. Higher and lower respiration rates may be tailored slightly to accommodate the abilities of participants. During both phases of varying respiration rate (items 1-9 in above table) and varying tidal volume (items 10-17 in above table), both respiration rate and tidal volume will be tracked from the reference device.

Readings will not be considered "successful" or "complete" unless all CPM device errors are resolved prior to the device streaming mode. In the case that a contact or tilt error cannot be resolved, the measurement must be repeated until the data quality is deemed sufficient. If the device begins peeling off of the skin during a measurement (as noted by a participant or by a study staff) and the streaming data quality looks questionable, the measurement must be repeated and the adhesives replaced to ensure good contact. It is recommended that if the electrode contact issues are cumulatively encountered three times, adhesives must be replaced to restore good device attachment to the body. The IFU can be followed for troubleshooting tips regarding issues with data quality. The device may have to be replaced, the skin moisturized, or the adhesive on the device replaced. Any note regarding measurement issues and steps taken to resolve these issues must be noted in the CRF. If the above actions were not taken, the relevant readings should be excluded based on the deviation of the study protocol.

The recorded capnography waveforms, simultaneously acquired with the CPM readings for Items 1-17, will be interpreted by clinicians in a blinded fashion to provide the measured respiration rate as a reference. After time synchronization between the capnography and the CPM system, the sponsor will provide the clinicians with segments in the continuous capnography waveform corresponding to the duration of the CPM system readings. Clinician(s) will then be asked to annotate and provide the reference respiration rate.

Discontinuation/withdrawal of participants from the study:

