Account, member, certificate or professional license numbers, health beneficiary numbers		

Vehicle identifiers and serial numbers, including license plate numbers		
Check 'None' when none of the identifiers listed above will be recorded, maintained, or shared during the conduct of this study. (exempt category 4)	 None	 None

Data Analysis

Power analyses may not be appropriate if this is a feasibility or pilot study, but end-point analysis plans are always appropriate even if only exploratory. Provide all information requested below, or provide justification if not including all of the information.

Power Statement:

Population Justification:

We have determined that healthy volunteers should be sufficient to validate the metrics of tidal volume and respiratory rate, due largely to the fact that healthy volunteers are able to breathe through a range of respiration rates and tidal volumes without putting their health at risk. Using the intended use population, who are generally ailing, struggling to breathe normally, and elderly, we would likely not be able to cover the full range of measured values with as much standardization as we would like to in this protocol. The mode of operation of the device and its use does not change whether a subject is healthy or part of our intended use population, and thus we believe that whether this data comes from healthy or ill volunteers does not matter in this case.

Sample Size Justification:

Based on prior studies data, the mean error (e.g., bias) of the respiration rate across 6 and 40 bpm ranges between -0.02 and -0.16 bpm, and the standard deviation of the error ranges between 1.74 and 3.31 bpm. To demonstrate the mean error is less than ± 1 bpm, we will use a worst-case scenario of the mean error of -0.16 bpm with a standard deviation of 3.31 bpm. For two-sided hypothesis testing with significance level ($\alpha=0.05$) and with 90% power ($\beta=10\%$), the minimum sample needed across 6-40 bpm is 202. Given that 9 readings will be collected per each participant, the minimum number of subjects is 23.

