[figure not shown]

Title: SAP0002 Clinical Statistical
Analysis Plan

NCT: NCT05445206

	Name	Role / Function	Signature	Date
Prepared By	[name]	Biomedical Systems Engineer		May 11 2022
Reviewed By	[name]	Algorithm Engineer		May 11, 2022
	[name]	Biomedical Engineer, Clinical Trial		May 12, 2022

Introduction:

This document describes the statistical analysis planned for the clinical evaluation data. The study is described in the clinical evaluation protocol (CEPR0002).

Analysis Plan:

Analysis 1: Respiration rate accuracy

The primary objective of this analysis is to demonstrate whether 85% of the errors are bounded within ± 2 bpm. It is noted that we will be using 85% instead of 95% because the CPM system is intended to give a trend, represented by multiple data points over time. This means the errors in the individual data points are averaged out in the trend interpretation, therefore justifying the change from 95% to 85%.

Respiration rate under natural breathing condition, if available, and controlled breathing condition (6, 10, 15, 20, 25, 30, 35, 40 brpm) will be summarized for CPM system and clinician annotated capnography. Although multiple breathing rates conditions are achieved within a subject, each data point is considered independent from each other. Prior look-ahead testing showed that there's no difference in mean errors and median errors across different breathing rate conditions, thereby justifying analyses after pooling all rate conditions together.

The error will be calculated by the difference between the CPM system's estimate and clinician annotated reference for each body posture. The error will be summarized using descriptive statistics and its limits of agreement. If the initial clinician's annotation is strongly suggested to be inaccurate by the compelling evidence (e.g., significant deviation from the simulated breathing or equivalently strong observations), the second annotator may be introduced to read the capnography waveform independently. The final respiration rate is determined based on two annotator readings.

Analysis 1-1: Respiration rate error descriptive statistics

The descriptive statistics includes but not limited to:

- Percentage of the CPM system's RR estimate not reported due to bad signal quality.
- Mean, median, variance, standard deviation, skewness, kurtosis, root mean squared error, and root median squared error.

Analysis 1-2: Percentage of respiration rate error within ± 2 brpm

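### Procedure C paces 15 BPM twice and 25 BPM not at all in items 2-9, so the four procedure versions are not reorderings of one set

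*Protocol*

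**What the plan says.** The protocol (Study Procedures) offers four versions of the breathing exercises and says of them: "Four different versions of the exercises (Procedures A-D) will be available that differ only in the sequence of the measurements". Each subject follows one version, chosen at random through the EDC; no allocation ratio or blocking is given.

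In the Procedure C table, item 4 reads "4 15 BPM Natural Doctor Setup, App 4 min" and item 8 reads "8 15 BPM Natural". The table's only 25 BPM entry is item 15: "15 25 BPM Natural".

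The protocol divides the session into phases of "varying respiration rate (items 1-9 in above table) and varying tidal volume (items 10-17 in above table"). On the reference rate it says: "The recorded capnography waveforms, simultaneously acquired with the CPM readings for Items 1-17, will be interpreted by clinicians". The Sample Size Justification for respiration rate states: "Given that 9 readings will be collected per each participant, the minimum number of subjects is 23". SAP Analysis 1 says that respiration rate under natural breathing, if available, and under the "controlled breathing condition (6, 10, 15, 20, 25, 30, 35, 40 brpm) will be summarized" for the device and for the annotated capnography. It then pools all rates for the accuracy analysis.

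**The concern.** If the versions differ only in order, every subject should provide the same set of rates whichever version is drawn. As printed, subjects on Procedure C do not. Because each subject follows a single version, the missing 25 BPM reading cannot come from another table.

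These are operational tables. Staff working from Procedure C as printed would collect an extra reading at 15 BPM and one fewer at 25 BPM, a rate that the SAP names for summary. The trial supports a 510(k) submission covering 6-40 BPM, where an unexplained uneven count at one rate would invite a question. What is at stake is the mix of rates. The number of readings and the success criterion do not change.

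**Working it through.** **1. Rates in items 2-9, from the four tables**

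| Version | Items 2-5 | Items 6-9 | 15 BPM | 25 BPM |
|---|---|---|---|---|
| A | 15, 30, 40, 6 | 25, 10, 35, 20 | 1 | 1 |
| B | 30, 40, 6, 15 | 10, 35, 20, 25 | 1 | 1 |
| C | 40, 6, 15, 30 | 35, 20, 15, 10 | 2 | 0 |
| D | 6, 15, 30, 40 | 20, 25, 10, 35 | 1 | 1 |

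A, B and D each hold 6, 10, 15, 20, 25, 30, 35 and 40 once. No reordering of that set gives C.

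**2. Is it one cell or a different design?** From A to D, each block of four items (2-5, 6-9, 10-13, 14-17) rotates by one place. That gives 16 items × 4 versions = 64 cells. Of these, 63 fit the rotation, and Procedure C item 8 is the only one that does not. Items 14-17 hold 10, 15, 25 and 30 BPM once in every version, and items 10-13 hold the four breathing depths once in every version.

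**3. Sample size figure.** With mean error 0.16, SD 3.31 and margin 1 bpm, the stated 202 is reproduced when the type II error is split over two sides: [3.31 × (1.960 + 1.645) / (1 − 0.16)]² = 201.8, rounded up to 202. Then 202 / 9 = 22.4, rounded up to 23 subjects. A Procedure C subject still gives nine readings in items 1-9, so neither figure changes.

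**4. Readings per rate and posture.** Assumption: 40 subjects and equal selection probability, so 40 / 4 = 10 are expected on C. With n_C subjects on C:

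- All paced items (2-9 and 14-17): 25 BPM has 80 − n_C readings and 15 BPM has 80 + n_C.
- Items 1-9 only: 40 − n_C and 40 + n_C.

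| Subjects on C | All paced items, 25 / 15 BPM | Items 1-9, 25 / 15 BPM |
|---|---|---|
| 10 (expected) | 70 / 90 | 30 / 50 |
| 5 (2.5% quantile) | 75 / 85 | 35 / 45 |
| 16 (97.5% quantile) | 64 / 96 | 24 / 56 |

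The quantiles are those of a binomial distribution with 40 trials and probability 0.25. At the expected split, 25 BPM loses 10 / 80 = 12.5% or 10 / 40 = 25% of its readings. An interval at that rate, if one were computed, would be wider by a factor of √(80/70) = 1.069 or √(40/30) = 1.155.

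**5. Effect on the pooled proportion.** The pools here include the natural-rate items: 40 × 17 = 680 readings per posture for items 1-17, or 40 × 9 = 360 for items 1-9. The share of readings that change rate is 10 / 680 = 1.47% or 10 / 360 = 2.78%. If the proportion within ±2 bpm differed by 10 points between 15 and 25 BPM (an assumption), the pooled figure would move by 0.0147 × 10 = 0.15 points or 0.0278 × 10 = 0.28 points.

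**The case against.** The strongest reply is that nothing inferential depends on this cell. Success rests on one pooled proportion, no criterion or interval is set per rate, and the SAP justifies pooling by reporting no difference in mean or median error across rates. On that premise, swapping one rate for another is immaterial. This stands, and it is why the point is minor.

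The counts over all paced items are also unequal by design: 10, 15, 25 and 30 BPM are each paced twice per subject, and 6, 20, 35 and 40 BPM once. Even with the discrepancy, 25 BPM has 70 readings against 40 at each of those four rates. This also stands. An otherwise even allocation is disturbed only if Analysis 1 is confined to items 1-9. The documents do not settle that: the phase description and the nine readings point to items 1-9, while annotation of items 1-17 points the other way.

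Three smaller points are fair. The SAP lists the rates to be summarised but does not specify a per-rate error table. The EDC content cannot be seen, so it may not repeat the printed cell. The text was read from PDF by a program, so the row should be checked in the source, although it shows no damage.

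None of this reconciles the tables with the statement about them. The allowance to tailor higher and lower rates slightly to a participant's abilities does not explain a printed 15 in place of 25.

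**Conclusion.** The concern holds as a minor inconsistency. Procedure C departs from the other versions in one cell, item 8, and the statement that only the order differs is untrue as printed. No subject lacks 25 BPM altogether, because item 15 of Procedure C paces it with annotated capnography. If only items 1-9 enter Analysis 1, however, Procedure C subjects contribute nothing at that rate.

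With 40 subjects and an assumed equal split, 25 BPM loses 10 readings per posture and 15 BPM gains 10. The pooled primary proportion moves by at most about 0.3 points under the assumed 10-point difference between the rates. The sample size is unchanged, and so is Analysis 2, since items 10-17 hold the same eight conditions in every version.

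**What to change.** Reconcile item 8 of Procedure C with the Study Procedures statement, the other three tables and the SAP rate list, so that all four versions contain the same set of rates. The sponsor should confirm which entry was intended, and check whether the EDC and case report form carry the same cell. For subjects already run on Procedure C as printed, analyse each reading at the rate actually paced and report the number of readings per rate. Separately, one SAP sentence naming the items that enter Analysis 1 would settle whether item 15 counts.

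The cost is a one-cell protocol correction, a matching EDC correction if the check shows one is needed, and that sentence. No visits, readings or subjects are added.

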In addition, based on the prior study, the root mean squared residual relative errors after linear fitting ranges between 25.2 and 30.4%. To demonstrate that the root mean squared residual errors after liner fitting is less than 35% based on the hypothesis testing Chi-squared test with significance level ($\alpha=0.05$) and 95% power ($\beta=5\%$), the minimum sample needed is 136. Given that 8 readings will be collected per each participant, the minimum number of subjects is 17.

However, to better reflect a broader patient population and since we might be under-estimating our error, we plan to enroll 40 subjects (up to 60 subjects, if necessary).

Data Analysis Plan:

Demographics:

A table will be constructed with counts and percentages of the number of subjects who were screen failures, the number of subjects enrolled in the study, the number of subjects withdrawn from the study before study completion, and the number who completed the study. For those subjects who withdrew before completion of the study, counts and percentages of the reasons for withdrawal will be tabulated. The continuous demographic characteristics at screening will be summarized for all subjects enrolled in the study using descriptive statistics (mean, standard deviation, median, minimum, maximum, and number of non-missing observations). The categorical baseline characteristics will be summarized for the study participants using frequency counts and percentages.

Effectiveness and Endpoint Analyses:

Respiration rate and relative tidal volume from the CPM System will be derived from the CPM analytics engine as described previously in the protocol, and the equivalent parameters and study data will be recorded from the reference device output. The reference respiration rate will be derived by trained medical professional annotating the number of breathing cycles in the recorded capnography waveform in the time period corresponding to the CPM readings.

For pairs of respiration rate calculated by the CPM and the reference, Bland-Altman analysis will be conducted to evaluate the accuracy of the respiration rate.

For pairs of relative tidal volume (rTV) calculated by the CPM system and tidal volume measured by the reference device, the correlation coefficient and R^2 value for the tidal calculated. In addition, the root mean squared of the residual errors after linear fitting will be calculated to characterize the relative errors of the relative tidal volume.

Endpoints:

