Respiration Rate Accuracy

- 85% respiration rate error $\leq \pm 2$ BPM between reference and test device at 6-40 BPM

Relative Tidal Volume Relative Accuracy

- Root Mean Squared (RMS) of residual error after linear fitting $\leq 35\%$

Respiration Rate Endpoint Justification

The Respiration Rate is derived by the CP Analytics Engine from impedance measurements taken by the CPM device for a one (1) minute period. The CP Analytics Engine performs a quality control (QC) check for at least 30 seconds of consecutive impedance measurement samples. This QC-validated measurement data of at least 30 seconds results in a maximum computational accuracy of 2 BPM for the respiration rate. Consequently, an accuracy of 2 BPM is deemed sufficient for the CPM Device's intended use.

Relative Tidal Volume Endpoint Justification

Relative Tidal Volume as measured by an implanted device have shown to have day-to-day variability ranges between 10% and 14% in terms of coefficient of variation (Boehmer et al., *Journal of Cardiac Failure*, vol. 18, no. 8S, Aug, 2012). In addition, breath-to-breath tidal volume variability ranges from 18% to 43% depending on the underlying pulmonary disease conditions (Kuratomi et al. *Japanese Journal of Medicine*, vol. 24, no. 2, May, 1985), which further supports that day-to-day variability can be as high as 14%. Given this physiological day-to-day variability, it is considered that as high as 35% (about 2.58 times, $Z_{99.5\%}$, of 14%) of change can be

considered physiologic unless other clinical information strongly indicates otherwise. To correctly indicate the change greater than 35%, the relative error less than 35% is deemed sufficient to trend and indicate clinically significant change of rTV.

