Using the data that are classified by the CPM system as good quality, the percentage of the respiration rate whose error is within ± 2 brpm is derived. The confidence interval for the proportion of the errors within ± 2 brpm will also be characterized assuming that the number of data points whose errors are within ± 2 brpm follows binomial distribution.

Analysis 1-3: Respiration rate error limits of agreement

The limits of agreement will be derived using a conventional Bland-Altman analysis as well as non-parametric approach in case the distribution of the error has a long-tail, significant deviation of Normality assumption of the conventional Bland-Altman analysis.

The 85% limits of agreement (bias \pm 1.44 standard deviation) will be tabulated. The 95% confidence interval for the limits of agreement will also be derived. In case the kurtosis, calculated in the Analysis 1-1, is high indicating that the distribution of errors has a long tail, non-parametric limits of agreement will also be presented to correctly characterize the range which 85% of the errors are expected to be bounded by. The non-parametric 85% limits of agreement will also be derived based on 7.5% and 92.5% percentile of the errors. The 95% confidence interval for non-parametric limits of agreement will be derived using a bootstrap resampling method.

Analysis 1-4: Other respiration rate accuracy analyses

A 95% confidence interval (CI) for mean error (i.e., bias) will be tabulated. While the primary objective is to show that the CPM estimate is accurate within ± 2 brpm, the CI for mean error will additionally show if there is any systemic bias in the CPM estimate. The standard deviation of the paired differences will also be tabulated.

If the lower bound of the 95% confidence interval for the percentage of the errors within ± 2 bpm from Analysis 1-2 exceeds 85%, it is demonstrated with statistical significance that the CPM system's respiration rate accuracy is sufficient in comparison to the reference to support its intended use. Also, the other analyses should provide different lenses to characterize the respiration rate accuracy.

Analysis 2: Accuracy of relative changes of relative tidal volume

The primary objective of this analysis is to demonstrate the CPM system's relative tidal volume (rTV) is accurately tracking true changes in tidal volume (TV).

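### The respiration-rate sample size and its 90% power are for mean error within ±1 bpm, not for the primary rule on the proportion of errors within ±2 bpm

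*Protocol*

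**What the plan says.** **Sizing.** The Protocol, Sample Size Justification, gives a prior mean error of -0.02 to -0.16 bpm and an SD of 1.74 to 3.31 bpm. It then states its aim: "To demonstrate the mean error is less than ± 1 bpm, we will use a worst-case scenario". With bias -0.16, SD 3.31, two-sided alpha 0.05 and 90% power, it concludes that "the minimum sample needed across 6-40 bpm is 202". At 9 readings per participant it derives 23 subjects. Enrolment is set at 40, and up to 60 if necessary, to reflect a broader population and because the error may be underestimated. No calculation supports that step.

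**Primary endpoint.** The primary RR outcome measure in the Protocol is the proportion of errors within ±2 bpm. Under Endpoints, 85% of errors must be within ±2 "BPM between reference and test device at 6-40 BPM".

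**Decision rule.** The SAP's rule for Analysis 1, stated at the end of Analysis 1-4, begins "If the lower bound of the 95% confidence interval for the percentage of the errors within" ±2 bpm and requires that bound to exceed 85%. Analysis 1-2 uses readings that the device classifies as good quality and a binomial distribution. Analysis 1 adds that "each data point is considered independent from each other", and takes the error against the "clinician annotated reference for each body posture".

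**Mean error.** Bland-Altman analysis is a secondary outcome in the Protocol. In SAP Analysis 1-4, "the CI for mean error will additionally show if there is any systemic bias in the CPM estimate". Neither place sets a ±1 bpm limit.

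**The concern.** The hypothesis that was powered is not the one that decides the study. A small mean error and a high proportion of small errors are different properties: a device can have almost no bias and still miss ±2 bpm often. The stated 90% power therefore says nothing about the chance of meeting the primary RR endpoint, and a reader cannot tell whether 40 subjects are enough. The relative tidal volume part of the same section is sized on its own criterion (residual error below 35%) from a prior estimate of that quantity, so the RR part is the exception.

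At stake is a failed or inconclusive validation. The mismatch does not raise the risk of a false claim of accuracy.

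**Working it through.** **1. The plan's own figure.** Inputs from the Protocol: SD 3.31, bias -0.16, margin 1, so the distance to the nearer margin is 1 - 0.16 = 0.84.

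n = [(1.960 + 1.645) × 3.31 / 0.84]² = 201.8, rounded up to 202; 202/9 = 22.4, rounded up to 23 subjects.

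The value 1.645 corresponds to beta/2 = 0.05. With 1.282 (beta = 0.10) the formula gives 164. The arithmetic is sound and slightly conservative, but for mean error.

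**2. The rule that decides the endpoint.** Success requires the lower two-sided 95% limit of x/n to exceed 0.85. I use the exact (Clopper-Pearson) limit and treat readings as independent, as the SAP does. The smallest passing x follows from the beta quantile at 0.025 with parameters x and n - x + 1. Power is the binomial probability of at least that x. The documents give no true proportion, so a range is assumed.

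| Readings | x needed | Power at 86% | at 88% | at 90% | True proportion for 90% power |
|---|---|---|---|---|---|
| 360 (40 × 9) | 320 (88.9%) | 6% | 34% | 79% | 90.7% |
| 720 (40 × 9 × 2 postures) | 631 (87.6%) | 11% | 64% | 98% | 89.1% |
| 1,360 (40 × 17 × 2) | 1,182 (86.9%) | 18% | 90% | >99% | 88.0% |
| 540 (60 × 9) | 476 (88.1%) | 8% | 49% | 93% | 89.7% |

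The Protocol counts 9 readings per subject. The SAP takes the error per posture, and the Protocol has capnography annotated for items 1-17. The plan does not say which of these counts applies.

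**3. What the prior bias and SD imply.** For normal errors, P(|e| ≤ 2) = Φ((2 - b)/s) - Φ((-2 - b)/s). The other shapes are assumptions scaled to the same SD; for the grids, the SD before rounding is reduced so that the rounded SD matches.

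| Error shape | b = -0.02, s = 1.74 | b = -0.16, s = 3.31 |
|---|---|---|
| Normal | 75% | 45% |
| t, 3 df | 86% | 63% |
| Normal, rounded to 1 bpm | 85% | 55% |
| Normal, rounded to 2 bpm | 93% | 64% |

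For normal errors with no bias, 85% within ±2 bpm needs an SD of 2/1.44 = 1.39 bpm, below the lowest prior SD quoted. At a true 85.5% to 86%, power is about 4% to 18% across 360 to 1,360 readings. At a true 93.2% it is 99.9% with 360 readings.

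**4. Clustering.** The documents give no within-subject correlation, so I assume 0.05, 0.10 and 0.20. For 40 × 9 readings at a true 90%, a beta-binomial simulation of the unadjusted SAP rule gives power of about 76%, 73% and 70%. If the limit were adjusted, the effective n is 360/(1 + 8 × correlation) = 257, 200 and 138, with power of about 66%, 47% and 37%.

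**The case against.** The strongest reply is that the plan may be adequately powered anyway.

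- **Error shape.** On a 2-bpm grid at SD 1.74 the proportion is 93%, and success is almost certain. The Protocol's endpoint justification, which gives a computational accuracy of 2 BPM from 30 seconds of data, lends this some support but does not establish such a grid. This stands: at the lower SD the outcome runs from near-certain failure to near-certain success. At SD 3.31, which the Protocol itself plans on, every shape tried stays between 45% and 64%.
- **Quality filter.** Analysis 1-2 keeps only good-quality readings, and the Protocol does not say whether the prior SDs were filtered the same way. This also stands, and only the prior data can settle it.
- **Reading count and enrolment.** Per-posture errors and items 1-17 point to more than 360 readings, and 60 subjects are allowed. With 60 subjects and both postures (1,080 readings), power is 80% at a true 88%. These are fair scenarios, but the plan commits to none of them.
- **Choice of limit.** The SAP says only binomial. Wald limits at 360 readings need 318 and give 87% power at a true 90%. This is a modest gain.
- **Clustering.** The correlations are assumed, and the adjusted limit is not in the SAP. The clustered figures are a sensitivity check, and the conclusion does not need them.

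None of these points supplies a power for the 85% rule.

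**Conclusion.** The concern holds and should be fixed. The 202 readings, 23 subjects and 90% power belong to a ±1 bpm mean-error hypothesis that decides nothing in either document; the primary RR rule has no stated power. At 40 subjects, 90% power needs a true proportion within ±2 bpm of 88.0% to 90.7%, depending only on which readings count. This assumes exact limits and independent readings.

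If the true proportion is 92% or more, 40 subjects suffice under the same assumptions (98.5% power at 360 readings). The quoted bias and SD raise serious doubt that it is that high, but they do not prove failure, because the proportion depends on the error shape and on the quality filter.

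**What to change.** In the Sample Size Justification, replace the RR power statement with one for the SAP rule: lower two-sided 95% limit of the proportion within ±2 bpm above 85%, at 40 subjects. The statement should:

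- take the observed proportion within ±2 bpm and its within-subject correlation from the same prior studies, on readings that pass the device's quality check;
- state which readings count (items 1-9 or 1-17, one or both postures) and which binomial interval is used;
- give the smallest true proportion that yields 90% power;
- say so, before data are analysed, if the prior proportion is at or below 85%.

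Delete the ±1 bpm calculation or label it as supporting Analysis 1-4 only.

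The cost is one recalculation from prior data that the sponsor cites, plus a wording change. The stated power may be less favourable. The fix itself needs no added subjects or procedures.
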